10.1 Parameter values

To the extent that it is possible given the estimates available, we have strived to base the choice of parameter values on evidence. However, it must be acknowledged that, as is often the case with power calculations, the evidence is often lacking or meagre, and we often must resort to guesstimates. In doing so, we have endeavoured to err on the side of conservatism and have conducted sensitivity analyses.

Power

Power is set to 80% and statistical significance to 5%.

Minimum detectable effect size

We calculate the sample size necessary to detect a small effect size (δ) defined as 0.2 standard deviation (SD) units (Cohen 1992). Consider our main outcome i) – the 10-year risk of a heart attack or stroke predicted by the office-based Globorisk algorithim. Given an estimated mean 10-year CVD risk of 11.35% in the control group, which we obtain from Globorisk for individuals aged 40-69 with mean values of all risk factors, if the standard deviation is one fifth of the mean, then an effect size of 0.2 SD corresponds to a 4% reduction in the mean. The assumption that the standard deviation is one fifth of the mean is based on estimates of the distribution of 10-year CVD risk scores (Gale et al 2014; Gray et al 2014). However, we caution that these estimates are not obtained using the Globorisk algorithm and most are for samples of high-income country populations.⁷

We deliberately choose a small effect size in order to ensure that our samples will be sufficient to detect only marginal impacts of the interventions on the risk factors that determine the CVD risk prediction. The logic is threefold. First, risk factors such as smoking and weight are notoriously hard to influence. Second, our information intervention is of unknown effectiveness and we recognize a possibility that a non-negligible fraction of respondents are unable to absorb the information provided on their CVD risks. Third, while the procedures defined by the PhilPEN protocol are proven to be effective, our aim is to establish effectiveness as the program is implemented, which may fall well short of the stipulated testing, medication and counselling.

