For mean systolic blood pressure (outcome iii), mean BMI (v) and mean waist circumference (viii), we obtain the estimated control group means from measures taken in the 2013 National Nutrition Survey (NNS) for individuals aged 40-69 (FNRI-DOST, 2015). The standard deviation is assumed to be one seventh of the mean for systolic blood pressure, one fifth of the mean for BMI and one ninth of the mean for waist circumference based on Ezzati et al (2004). In each case, we set the minimal detectable effect size to 0.2 SD units of the mean.

Control group proportions for elevated blood pressure (outcome iv), overweight/obese (vi), smoking (vii), central adiposity (ix), undiagnosed hypertension (x) and hypertension medication (xi) are also taken from the 2013 NNS for individuals aged 40-69. For these binary outcomes, we set the minimal detectable effect size to the small value defined by Cohen (1992) as 0.2 of his h-index.

Intra cluster correlation

⁷ Using the Framingham algorithm for 10-year CVD risk (D'Agostino et al 2008), Gale et al (2014) report a mean of 14.3% and a standard deviation of 2.59 for an English sample of 60+, non-frail persons with no history of CVD. A small study of 40+ employees without previous CVD in a region of Wales reports means (standard deviations) of non-laboratory based Framingham 10-year CVD risk of 10.7% (2.4) for males and 4.8% (1.2) for females (Gray et al 2014).

To the best of our knowledge, there are no estimates available of the intra cluster correlation for (predicted) 10-year CVD risk with clusters defined by communities resembling the size of Filipino barangays. Some idea of the correlation is given by ICCs for CVD risk factors, which determine predicted risk. Table 3 provides estimates of such ICCs for clusters defined at the level of primary care practice obtained from three North American studies.

While homogeneity of CVD risk factors within Filipino barangays need not necessarily closely resemble the homogeneity observed within primary care practices in North America, these estimates at least give an idea of the ICC that might be expected. We set the ICC at 0.1, which is almost twice the highest estimate for any risk factor in Table 3. This is even more conservative than might appear at first sight since one would expect there to be even less within community homogeneity in CVD risk predicted on the basis of all risk factors than there is in each individual risk factor individually.

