Table 3 Estimates of intra cluster correlation coefficients for CVD risk factors at the level of primary care practices in North America

	Eastern Ontario	Rhode Island and Massachusetts	Vermont				
	Singh et al (2015)	Parker et al (2005)	Littenberg & MacLean $(2006)^{\pm}$				
Systolic Blood Pressure	0.054	0.047	0.042				
Low Density Lipoprotein	0.035	0.006	0.045				
Fasting Blood Glucose	0.023	0.016	N/A				
Body Mass Index	N/A	0.031	0.011				
Smoking	N/A	0.036	0.005				

 \pm Individuals with diabetes only.

For all other outcomes, we also assume an ICC of 0.1 in our baseline power calculations and test sensitivity to revising the value downward to 0.05.

Cluster size

We aim to observe 10 individuals within each cluster at follow-up who have been exposed to an intervention (or are in the control group). To achieve this, we sample a larger number at baseline to allow for attrition and non-eligibility for the lottery intervention. This cluster size is set to achieve a balance between constraining the sample size while limiting costs incurred by surveying in many barangays.

Autocorrelation in outcomes

We will estimate treatment effects using ANCOVA. That is, the post-treatment outcome observed at follow-up will be regressed on an indicator of treatment group membership and the pre-treatment outcome, plus covariates observed at baseline. The coefficient on the treatment indicator is the estimated treatment effect. For given power and minimal detectable effect size, the required sample size is decreasing with the autocorrelation of the outcome (as well as the proportion of its variance that can be explained using baseline values of covariates).

Estimates of the autocorrelation in predicted 10-year CVD risk are not available, as far as we are aware. Age, sex, smoking and BMI, four of the five predictors of CVD risk used by Globorisk, are obviously very highly autocorrelated. The fifth predictor -a single visit measure of blood pressure -can be

expected to display much lower serial correlation. Blood pressure can vary depending on recent activity and diet, although we will follow a standard protocol for its measurement. It may also vary with the enumerator, although this will be minimized by use of an electronic meter and we can control for enumerator effects.

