In addition to the baseline value of the outcome, we will also control for a very larger battery of baseline covariates, including socioeconomic characteristics, medical history, health behavior and knowledge of risk factors.

Admittedly, we do not have a good idea of how the follow-up outcome will vary with all of these factors. We assume for the main power calculations a correlation of 0.6, which corresponds to an explained variance of 0.36. This would seem to err on the side of conservatism, given the very extensive set of covariates that can be used. We use the same value for all outcomes. We test sensitivity of the required sample size to reducing the autocorrelation to 0.4.

Attrition rate

We assume an attrition rate of 10%. This seems reasonably conservative given that the follow-up survey will be only 6-7 months after the baseline and we will make efforts to track respondents in the interim period. This will consist of obtaining the cellphone/ contact numbers of all respondents during the baseline interview. We shall instruct our survey contractor to develop and execute a plan to trace the respondents in between surveys. Their tracing strategy must include contacting each respondent at least once, and possibly twice, during the interim period to check if the respondents are still in the same location. Contact will be through a SMS, a telephone call and, if necessary, a personal visit. We will also engage a local field coordinator (other than the survey firm) to help out in validating the tracing reports of the survey firm, and in coordinating with Barangay Health Worker (BHW) or barangay captain about the whereabouts of respondents that we cannot locate.

Adjustment for refusal, ineligibility and item non-response

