Individuals who report a diagnosis of heart disease, heart attack, stroke or diabetes, or who are taking medication for hypertension or diabetes will be ineligible. We must first screen the initially sampled individuals to identify these cases. Using data from the NNS, we estimate this group will amount to 14% of those initially sampled. Other sampled individuals will be eligible but will refuse to give consent to participate. We assume 15% of those sampled will not give their consent. Costs will be incurred performing the initial screening of sampled households before the ineligible and non-consenting cases are identified. We adjust the initially selected sample upwards to allow for these non-usable respondents. A similar adjustment is made for an assumed 5% of the eligible sample who will not answer all requisite questions or complete all measurements despite initially giving consent.

Compliance rate

Not all respondents who are offered a voucher will go to a RHU/CHC for a checkup and so get the lottery ticket to which they are entitled. And some of the control group will go to the RHU/CHC despite not being offered any inducement. We have no firm evidence on which to hazard a guess about the extent to which the offer of a lottery ticket will be effective in persuading people to go for a checkup. Based on the facts that the offered prize of P5000 (US\$100) is roughly equivalent to 14 days' earnings at the average wage in the province, and from discussions with health workers in the area, we believe that response will be high. We assume a compliance rate of 60% and conduct sensitivity analysis setting this as low as 50%.

Table 4 summarises all the parameter values used in the various scenarios considered in the power calculations.

Parameters	Scenario 1 (main)	Scenario 2	Scenario 3	Scenario 4	Scenario 5
Significance level (α)	0.05	0.05	0.05	0.05	0.05
Power $(1-\beta)$	0.8	0.8	0.8	0.8	0.8
Minimum detectable	0.2	0.2	0.2	0.2	0.2
standardized effect size (δ)					
Attrition rate	0.1	0.1	0.1	0.1	0.1
Refusal to consent rate	0.15	0.15	0.15	0.15	0.15
Item non-response rate	0.05	0.05	0.05	0.05	0.05
Ineligibility rate	0.14	0.14	0.14	0.14	0.14
Average cluster size at follow-up	10	10	10	10	10
Intra-cluster correlation	0.1	0.05	0.1	0.05	0.1

Table 4 Parameter values used in power calculations

Autocorrelation in outcomes	0.6	0.6	0.6	0.6	0.4	
Compliance rate in lottery intervention	0.6	0.6	0.5	0.5	0.6	

	Control group	Treatment group	
Mean CVD risk	11.35	10.89	

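### Is the 4% detectable fall in mean predicted CVD risk unsound because it takes the SD as one fifth of the mean and never varies it?

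*Combined protocol and SAP*

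**What the plan says.** Section 10.1 sets the minimum detectable effect at 0.2 SD, with 80% power and 5% significance. For predicted 10-year CVD risk it starts from a control mean of 11.35% and states that "if the standard deviation is one fifth of the mean, then an effect size of 0.2 SD corresponds to a 4% reduction" in the mean. It gives its basis: "The assumption that the standard deviation is one fifth of the mean is based on estimates of the distribution of 10-year CVD risk scores". It then limits that basis: "we caution that these estimates are not obtained using the Globorisk algorithm and most are for samples of high-income country populations". The opening of the section also concedes that evidence for the inputs is thin and that several of them are guesses.

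Footnote 7 prints the source figures. One study has "a mean of 14.3% and a standard deviation of 2.59 for an English sample of 60" and over, non-frail and free of CVD. The other is a small study of employees aged 40 and over without previous CVD, with means (SDs) of "10.7% (2.4) for males and 4.8% (1.2) for females".

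On the outcome correlation the section says "Estimates of the autocorrelation in predicted 10-year CVD risk are not available, as far as we are aware". It adopts 0.6, commenting "This would seem to err on the side of conservatism, given the very extensive set of covariates that can be used". On the scenarios, "Table 4 summarises all the parameter values used in the various scenarios considered in the power calculations". That table varies the intra-cluster correlation (ICC), compliance and outcome correlation, holds the effect at 0.2 throughout, and has no row for the SD. Section 10.2 sets the sample size from the binary outcomes.

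**The concern.** The 4%, or 11.35 to 10.89, is the only place where the plan says in units of risk what it can detect on its principal outcome, and a null result would be read against it. It rests on one ratio. The two cited sources do not match the trial, which enrols both sexes aged 40 to 70: one is restricted to age 60 and over, the other is reported separately by sex. The caution in the main text mentions only the algorithm and country income. Both ratios from the study that starts at age 40 exceed one fifth.

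If 4% is held fixed as the target and the ratio is really 0.25, power at the adopted size falls from 81% to 62%. With the sexes pooled the ratio is larger still. The plan says it ran sensitivity analyses, yet none touches the SD.

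**Working it through.** **1. The plan's own figure.** SD = 11.35/5 = 2.27, and 0.2 × 2.27 = 0.454 points, which is 4.0% of 11.35. The treated mean is 10.896; Table 5 prints 10.89, a difference of 0.46 points or 0.46/2.27 = 0.2026 SD. With two-sided 5% and 80% power (1.96 + 0.84 = 2.80):

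- unadjusted n = 2 × (2.80 × 2.27/0.46)² = 382.3 per arm
- design effect 1 + 9 × 0.1 = 1.9; ANCOVA factor 1 − 0.6² = 0.64
- 382.3 × 1.9 × 0.64 = 464.9, rounded up to 47 clusters of 10 = 470
- divided by compliance squared, 470/0.36 = 1,306, as in Table 6

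The information arm follows from 1/n = 2/470 − 1/1,306, giving 287, also as in Table 6.

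**2. What the cited sources imply.**

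| Source | SD/mean | 0.2 SD as % of mean | Points on 11.35 | Treated mean |
|---|---|---|---|---|
| English sample, 60+ | 2.59/14.3 = 0.181 | 3.62% | 0.411 | 10.94 |
| Plan | 0.200 | 4.00% | 0.454 | 10.90 (printed 10.89) |
| Employees 40+, men | 2.4/10.7 = 0.224 | 4.49% | 0.509 | 10.84 |
| Employees 40+, women | 1.2/4.8 = 0.250 | 5.00% | 0.568 | 10.78 |

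One source lies below one fifth and two figures lie above it. The largest departure from 0.454 is 0.568 − 0.454 = 0.11 points.

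**3. Does the SD drive the sample size?** With the effect fixed at 0.2 SD, n = 2 × (2.80/0.2)² = 392.4 whatever the SD. The same chain gives 48 clusters, 480/0.36 = 1,333. Table 6 shows this directly: systolic pressure is planned with an SD of one seventh of the mean and waist circumference with one ninth, yet both need 1,333. The 1,306 for CVD risk differs only through the rounding of 10.896 to 10.89. A scenario with another SD would return the same number.

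**4. What 1,361 per arm detects.** In SD units, SE = √((2/1,361) × 1.9 × 0.64) = 0.0423, and the detectable effect is 2.80 × 0.0423/0.6 = 0.197 SD. As a share of the mean:

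| SD/mean | ICC 0.1, correlation 0.6 | ICC 0.1, correlation 0.75 | ICC 0.05, correlation 0.6 | Power for a fixed 4% (ICC 0.1, correlation 0.6) |
|---|---|---|---|---|
| 0.18 | 3.6% | 3.0% | 3.1% | 88% |
| 0.20 | 3.9% | 3.3% | 3.4% | 81% |
| 0.22 | 4.4% | 3.7% | 3.9% | 72% |
| 0.25 | 4.9% | 4.1% | 4.3% | 62% |

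**5. Pooling the sexes.** The male share is not in the documents; assume 50%. The mean is 7.75, within-sex variance 0.5 × 2.4² + 0.5 × 1.2² = 3.60, and between-sex variance 0.25 × 5.9² = 8.70. Total SD/mean is √12.30/7.75 = 0.45. Adjusting for sex removes the between-sex part, leaving √3.60/7.75 = 0.245, close to the women's row above. The detectable reduction is then 4.8% at a within-sex correlation of 0.6 and 4.0% at 0.75. Over an assumed male share of 30% to 70%, the figures are 4.7–5.0% and 3.9–4.1%.

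**The case for a change.** The best case for the concern is that the ratio was neither conservative nor tested. Only the 60+ sample falls below 0.20, the trial's age range begins at 40, and the main-text caution is silent on age and sex. That description is accurate, and a reader would learn slightly more from a range than from a single 4%.

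It does not amount to an error. The caution leads to footnote 7, which prints the age restriction, the split by sex, the small size of the second study and every mean and SD, so nothing needed for the check is withheld. The second study also matches the trial's lower age limit and its focus on people without previous CVD.

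The power figures of 62% and 72% answer a different question: they keep 4% as the target, whereas the plan's target is 0.2 SD. The 62% also applies a ratio for women alone to a trial of both sexes.

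The pooled ratio of 0.45 looks more damaging, since 0.2 SD would then be 9.1% of the mean. Combining it with a correlation of 0.6 is inconsistent, however. Spread that is purely between sexes is fully predictable from baseline: in the 50:50 example a within-sex correlation of 0.6 already implies an overall correlation of 0.90.

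What stands is that the true SD and correlation are unknown, so a shortfall against 4% is possible. It is not shown.

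**Conclusion.** The concern does not hold. The calculation is correct, its condition is stated, its sources are disclosed with their figures, and those figures bracket the assumed ratio. The sample size and the 80% power for 0.2 SD do not depend on the SD, and the adopted 1,361 exceeds the 1,306 calculated for this outcome because the binary outcomes set it.

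The uncertainty is confined to how 0.2 SD reads in risk units: 3.6% to 5.0% on the cited ratios, at most about 0.1 percentage point from the stated 0.45. A within-sex correlation of about 0.75 brings the detectable reduction back to 4% even with the by-sex ratios. Such a value is plausible, since the plan expects four of the five predictors to be very stable over time, but it is unverified. The ICC of 0.1, almost twice the highest value in Table 3 (0.054), and the omission of stratification add further margin. Restating the translation would alter no design choice, analysis or conclusion.

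This rests on ANCOVA adjustment for the baseline outcome and covariates as planned and, for the pooled-sex figures only, on the assumed male share of 30% to 70%.

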10.2 Results

Required sample sizes under the main scenario for parameter values described in the previous sub-section are given in Table 6. Estimates under alternative scenarios are given in Appendix B Tables B1-B4. The requisite sample size differs little across the outcomes but is slightly larger for the binary outcomes. We will set the sample size to that required to have sufficient power to test for the specified minimal effect size on the binary outcomes under the main scenario.

Table 6: Sample size calculations – Main scenario (1)

	Mean CVD risk	Mean systolic BP in mm Hg	Mean BMI	Mean waist circumference in cm	Binary outcomes
Required sample sizes					
Info treatment per round (unadjusted)	287	293	287	293	299
Lottery treatment per round (unadjusted)	1,306	1,333	1,306	1,333	1,361
Control per round (unadjusted)	1,306	1,333	1,306	1,333	1,361
Total baseline sample (adjusted)	4,816	4,916	4,816	4,916	5,019
Total follow-up sample	2,899	2,959	2,899	2,959	3,021
Number of clusters	290	296	290	296	303
Avg. cluster size at baseline	16.61	16.61	16.61	16.61	16.56

In implementing the sampling design, we will sample 303 barangays out of 849 distributed across the 32 municipalities and cities in Nueva Ecija province. We will meet with the mayors of all 32 municipalities to introduce the study, get their consent and endorsement of our field activities within their jurisdiction. This will be done during the field mobilization phase (see Table 2).

Since treatment will be randomized at the barangay level, there is no issue of contamination across households within a barangay. But since one RHU/CHC typically serves more than one barangay (there are 63 RHU/CHCs in the province), contamination through the same facility serving both treatment and control barangays needs to be considered. This is not an issue for the information intervention and control groups since the former does not require that the RHU/CHC do anything. The facility will be unaware of patients that belong to these two groups. There could be an issue if the role of the RHU/CHC in implementation of the lottery causes it to operate differently for all patients. One possibility is that it

improves implementation of the PhilPEN protocol across the board. Another is that the facility expends more effort on the patients entitled to enter the lottery, since it knows they are being monitored by the study, and neglects other patients. We will make efforts to avoid these reactions by encouraging the RHU/CHC to operate as it was and simply to issue the lottery tickets on completing a physical assessment of a patient presenting with a voucher. But even if the experimental effect cannot be completely avoided, it is not a major problem for the study. The lottery is used to provide random variation in go for a checkup at a RHU/CHC. This variation will be used to compare outcomes of those in the treatment group who go for a checkup with those in the control area who do not. We are not comparing outcomes of those who go for a checkup in the treatment and control barangays. So, even if the service improves for those in the control barangay, it does not invalidate our identification strategy.

11.Survey instrument

The baseline instrument contains a screening module to establish eligibility of the household and a main respondent for the study and interventions according to the inclusion/exclusion criteria described in section 9. Thereafter, two modules completed by the head of household, their spouse or another adult obtain information on housing conditions and ownership of assets that will be used to construct a wealth index. The randomly selected main respondent aged 40-70 will complete modules on socio-demographic characteristics, medical history, knowledge of CVD risk factors, health behaviour, CVD risk perceptions, general health (SF-36), health care utilization and expenses, work and earnings, and risk and time preferences.

To obtain incentive compatible measures of risk preferences, we offer different sets of choices in which respondents can win real money. Monetary incentives help to avoid potentially distorted measures of preferences due to self-serving biases, inattention and strategic motives that commonly arise in hypothetical choice experiments (Camerer and Hogarth, 1999). A commonly used and widely accepted procedure to implement real incentives in individual choice experiments is a random incentive system (Baltussen et al., 2012). In our study, we use a hybrid random incentive system in which only a randomly chosen subset of participants is selected after choices have been made and one of their choices is implemented. This procedure not only allows us to award sizeable nominal payoffs to a large sample of respondents while remaining within the project budget, but it also helps avoid income and portfolio effects that might occur if all tasks are paid out. We follow previous studies by randomly paying out 10% of the respondents (March et al., 2016). The maximum amount a respondent can earn is PHP 400.

Physical measurements of height, weight, waist circumference and blood pressure will also be obtained from the sampled individuals. Those allocated to the information treatment will be given a different risk perceptions module that provides information on average (for their age and gender) and predicted CVD risks. A final module completed by a barangay representative will collect information on proximity to health facilities.

The baseline survey instrument is attached as Appendix C.

The follow-up survey will be substantially shorter than the baseline instrument and will focus on obtaining data on outcomes.

12.Consent Process

The survey and interventions will not expose the study participants to any obvious potential harms. Nonetheless, we shall endeavor to take every precaution to protect the welfare of the participants. We will

secure the informed consent of all survey respondents – household respondent and main respondent – before the baseline interview. The consent forms state (see Appendix D):

- Study objective, investigators and funding source.
- The topics covered in the interview and its length.
- The physical measurements made (blood pressure, hip and waist circumferences, height and weight), with the assurance that the measurement will be temporarily stopped if the respondent is uncomfortable and resume only upon the consent of the respondent.
- Voluntary nature of the survey and right of respondent to stop the interview at any time.
- That follow-up survey to be conducted after 6-7 months.
- That confidentiality of the information shared and the identity of the respondent will be protected.
- That the respondent may ask for clarifications to the enumerator; or call study team members through the contact numbers or email provided for any complaint, question or clarification.
- That the respondent indicates consent by writing his/her name, signing over it and specifying the date in front of the enumerator.

The text of the consent form will be read by the enumerator before proceeding with the interview. Only when the consent form is signed by the respondent and the "consent and sign" option is ticked will the interview proceed.

Respondents in the lottery treatment group will be asked to sign an additional consent form to confirm their acceptance of the conditions under which the lottery will be conducted and they will be allowed to enter it. This includes information on what they must do to collect a lottery ticket from a RHU/CHC, which facility they must attend, by what date and how the winners will be informed (see Appendix D).

There is no separate consent form to confirm participation in the information treatment. This intervention does not involve the provision of any medical care, nor the offer of a financial reward on condition of seeking preventive care. Respondents are simply informed of the risk of heart attack/stroke within 10 years conditional on age, sex, blood pressure, BMI and smoking status. Respondents are told that these risks are estimated by doctors based on monitoring the health of thousands of individuals over many years. They are told that the estimates are specific to the Philippines.

A conformé letter of agreement will be sent to the mayor of every municipality or city from which barangays and households will be sampled. The letter contains information about the study, its objectives, proponents and funding source, and study activities (surveys and interventions) that will be undertaken. Additionally, the letter solicits the support and permission of the mayor to engage the local rural health unit/city health center in the lottery intervention. The tasks and responsibilities of the participating RHU/CHC are also laid out in an accompanying sheet. The letter assures the mayor that participation in the survey and interventions is voluntary, and informed consent of the participants will be sought first before the interview and participation in the intervention. Assurance will be given that participation of RHU/CHC will not generate any added cost to the local government, and that the study team will provide the lottery prize and take charge of delivering the prize money to the winner. The mayor will indicate his support and permission by signing the conformé.

13. Ethical issues

Data protection

To track respondents at follow-up, records of their names and addresses will need to be kept. These records will be kept on a secure computer in encrypted files accessible only by specified members of the immediate study team. Files containing names and addresses will not be shared by anyone outside of the study team. When data are made available to other researchers, respondents will be distinguished only by unique identification numbers and no names and addresses will be included in the data files.

Blood pressure information

Blood pressure will be measured using a digital monitor following standard procedures. It can be anticipated that some participants will have an elevated blood pressure reading that may warrant preventive actions. We will adopt the following protocol for dealing with elevated blood pressure readings:

- $140/90 \text{ mmHg} \le BP < 180/120 \text{ mmHg}$: Tell the respondent of the likelihood of hypertension, and advise to see a physician for confirmation. The information and advice will be recorded on an orange coloured card given to the respondent. Proceed with the interview.
- BP \geq 180/120 mmHG: Advise the respondent to proceed immediately to the nearest health facility. Issue a red coloured card with this advice. Stop the interview.

The BP thresholds specified above are slightly higher than standard recommendations to account for the fact that we will be using digital monitors, which are known to register higher BP readings than aneroid monitors.

Lottery intervention

A voucher will be given to the respondent, encouraging them to go for a checkup at their designated RHU/CHC. This intervention does not pose any risk to the respondents. It encourages them to seek preventive care.

The intervention is a one-time offer of a lottery ticket conditional on going for a checkup. Once the respondent goes for a checkup, then according to the PhilPEN protocol there should be continuity of risk assessment and, when needed, sustained management of CVD / diabetes. The protocol specifies the periodicity of risk assessments subsequent to an initial assessment/screening and the criteria for putting a patient on antihypertension/diabetes medications (Appendix A).

This group will not be informed of their Globorisk predicted CVD risk at baseline, although they will be told if their blood pressure is high (see above). At follow-up, the respondents in this group will be told their predicted CVD risk.

Information intervention

Each respondent in this group will be informed of their 10-year risk of heart attack or stroke for someone of the same age and sex as the respondent, and then conditional on the same age, sex, BMI, smoking status and blood pressure as the respondent. It will be emphasized that neither prediction is the risk precisely for the individual respondent. Rather, it will be pointed out that the risk varies with other factors not taken into account in the prediction.

There is also no issue of continuity of treatment since it is information that is provided, not medical care. At baseline, respondents in this group will not be informed that they can attend the RHU/CHC for a CVD risk assessment, although they are free to do so. At follow-up, they will be given this information. But they will not be offered the lottery incentive.

Control group

The information to be provided on 10-year risk of heart attack or stroke is publicly available from Globorisk. Hence, the control group can access this information. And the control group will be told the results of the physical measurements from which the CVD risk predictions are calculated. At follow-up, the control group will be told of the age, sex and risk factor conditional CVD risks.

